11.8.3 End of treatment

For patients of the control group no regular end of treatment has to be defined, since they are treated as usual.

For patients of the intervention group the **regular end** of treatment is reached when all components of the complex intervention are administered in accordance with the protocol.

For patients of the intervention group the **premature end** of treatment is reached when one or more components are lacking: Patients have the right to discontinue the treatment without giving reasons at any time and without losing the right to further treatment from the GP. If a patient does not arrive to an appointment, the GP must follow up the case until he has found out why the patient did not turn up. The GP must try to complete and document all the components of the complex intervention designated in the protocol. The documentation will continue in accordance with the protocol (intention-to-treat principle) accept the patient withdraws his/her written informed consent in the documentation of his/her data.

11.9 Schedule and expected duration of trial

- Pre-phase (development of all trial plans, materials and implemented instruments, ethics vote, study registration): 01/03/2010 to 30/06/2010
- First practice in – last practice out: 01/07/2010 to 30/10/2011

- First patient in – last patient out:	01/08/2010 to 30/10/2011
- Recruitment:	
a) Practices:	01/07/2010 to 31/12/2010
b) Patients:	01/08/2010 to 31/01/2011
- Database Cleaning, analyses and publication:	01/11/2011 to 29/02/2012
- Total study duration:	01/03/2010 to 29/02/2012

12 STATISTICAL CONSIDERATIONS

A detailed description of the statistical methods of this study will be provided in a Statistical Analysis Plan (SAP). Data analysis will be done blinded to treatment arm allocation (i.e. the treatments will be identified as 1 and 2 until analysis is complete). The primary analysis will be based on the 6-month follow-up data (T1).

12.1 Populations for analysis

The Intention-to-treat (ITT) population will consist of all randomised practices and their patients. Following the ITT principle, practices and their patients will be analysed in the treatment arms to which they were originally randomized, regardless of whether they refused or discontinued treatment, or whether other protocol deviations are known.

The Per-protocol (PP) population will consist of those ITT practices and patients with no major protocol violations. The criteria for the exclusion of practices or patients from the PP population will be determined by the study team at the latest before database lock.

12.2 Statistical hypotheses, methods, and analyses

The primary objective of this study is to determine the effectiveness of a complex intervention compared to usual care in multimorbid elderly patients, and to show that the complex intervention improves the appropriateness of prescriptions, as compared to usual care. The primary efficacy endpoint is the change in MAI score from baseline (T0) to 6 months after baseline (T1), i.e. the difference MAI T1–T0. The study objective will be statistically formulated as a test of the null hypothesis $H_0: \mu_1 = \mu_2$ (the mean difference MAI T1–T0 is equal in the two groups) against the alternative hypothesis $H_1: \mu_1 \neq \mu_2$ (the mean MAI T1–T0 are different in the two groups). The null hypothesis will be tested at the two-sided significance level of $\alpha=0.05$.

Because of the cluster randomisation, the primary efficacy analysis will use a multilevel regression approach with patients at level one and practices at level two. The primary model will include treatment group as fixed factor and practice as random factor. The results will be presented as the mean between-group difference in MAI T1–T0 with the corresponding 95% confidence interval. The associated Cohen's effect size d will be calculated. In addition, the practice related intraclass correlation coefficient (ICC) will be estimated. To support the primary analysis, all potentially relevant baseline characteristics at practice level (e.g. practice status) and baseline characteristics at patient level (e.g. MAI score at T0) will be added as covariates to the model in sensitivity analyses. Further sensitivity analysis of the primary endpoint will include an unadjusted two-sample t -test on change in MAI from baseline to 6 months after baseline. Results from these sensitivity analyses will serve to explain and interpret the results of the primary analysis.

The primary analysis will be performed adhering to the intention-to-treat principle. An additional sensitivity analysis will be conducted on a per-protocol analysis set.

Baseline characteristics of participating practices and patients will be described by treatment arm. Categorical data will be presented as frequencies and percentages. For continuous data, N, mean, standard deviation, median, inter-quartile range (IQR), minimum, and maximum will be provided.

The statistical analyses of the secondary endpoints will use the same multilevel approach as the primary analysis. All statistical tests will be two-sided at the significance level of $\alpha=0.05$. Because no adjustments for multiple endpoints are planned, findings will be interpreted with caution in view of the number of statistical tests undertaken. Only the result of the primary efficacy analysis will be interpreted in a confirmatory manner. Confirmatory subgroup analyses are not planned. No interim analysis with regard to efficacy will be done.

A complete case analysis will be performed. If any practices or patients are lost to follow-up, analyses will be done replacing the missing follow-up data with the last available or baseline data carried forward for that practice or patient.

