12.3 Sample size

Sample size was calculated using the primary endpoint, the change in MAI score from baseline (T0) to 6 months after baseline (T1), i.e. MAI T1–T0. Because high MAI scores indicate inappropriate prescriptions, a negative difference MAI T1–T0 indicates an improvement in the appropriateness of prescriptions for the target population. The MAI T1–T0 difference is assumed to be normally distributed in each treatment arm population and the variances of the group specific differences T1–T0 are assumed to be equal. In the preliminary analysis of PRIMUM pilot with a total of 60 patients from 12 practices, a mean MAI of 4.2 was observed at baseline. Three months later (i.e. 6 weeks after the intervention), the MAI in the intervention group decreased by 0.9 units, while the MAI in the control group decreased by 0.5 units. Thus, the resulting between-group difference was 0.4 in favour of the complex intervention. In a previous study of a similar patient population, between-group differences of 3 and 4 for changes in MAI from baseline to 3 and 12 months after randomisation were reported.³² However, the intervention in that study was even more intense than the intervention planned in PRIMUM. Thus, in the present study, a difference in the change values (MAI T1–T0) of at least 2 units between the treatment groups will be considered clinically relevant. In the PRIMUM pilot study, a pooled standard deviation of the MAI T1–T0 difference of 5.2 was observed. However, T1 was defined as 3 months from baseline, whereas in the present study, T1 is measured 6 months after baseline. Consequently, a greater standard deviation is expected for the MAI T1–T0 difference. Using the conservative assumption that the MAI scores at T0 and T1 are uncorrelated, we expect a standard deviation for MAI change of approximately 6 units. With this standard deviation, a between-group difference of 2 units corresponds to Cohen's effect size of $d=0.3$ and represents a small effect size.⁶³ Assuming an intraclass correlation coefficient (ICC) of 0.03 at practice level (which is also a conservative assumption because the ICC is assumed to be 0.01 in general practice setting⁶⁴) and assuming an average cluster size of 7 patients, we estimated a design effect of $DEFF = 1 + (7 - 1) \times 0.03 = 1.18$. Taking this design effect into consideration, a total of 62 practices and 434 patients (31 practices and 217 patients per treatment arm) will be required to detect a Cohen's d of 0.3 with a power of $1-\beta = 0.80$ using a two-sample t -test at a two-sided significance level of $\alpha=0.05$. The sample size calculation was performed using NCSS PASS 2008,

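### The confirmatory model for MAI change omits baseline MAI, which is valid but less precise than the baseline-adjusted model the plan keeps for sensitivity analyses

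*Protocol*

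**What the plan says.** Protocol section 12.2 defines the primary endpoint as MAI at 6 months minus MAI at baseline and specifies a two-level regression, patients within practices. On its terms it says: "The primary model will include treatment group as fixed factor and practice as random factor". The Statistics entry of the synopsis (1.4) names the same two terms.

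Baseline MAI appears one step later, in supportive work: "baseline characteristics at patient level (e.g. MAI score at T0) will be added as covariates to the model in sensitivity analyses". Section 12.2 gives those analyses the role of helping to interpret the primary result, and reserves confirmatory interpretation for the primary analysis alone.

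Section 12.3 sizes the trial on the change score. The pilot is reported thus: "a pooled standard deviation of the MAI T1–T0 difference of 5.2 was observed", at 3 months. For the 6-month endpoint the SD (in MAI units) is raised: "Using the conservative assumption that the MAI scores at T0 and T1 are uncorrelated, we expect a standard deviation for MAI change of approximately 6". The calculation then uses d=0.3, ICC 0.03 and 7 patients per practice, giving 31 practices and 217 patients per arm.

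Section 6 allocates practices 1:1 in randomly varying blocks and names no stratification factor. Sections 4 and 6 have baseline documentation completed in a practice before its allocation is disclosed.

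**The concern.** A change score subtracts the whole of the baseline value. Regression on baseline subtracts only the part that predicts follow-up. When the two scores are weakly correlated, full subtraction brings in more baseline noise than it removes. In the limiting case used for sizing ("Using the conservative assumption that the MAI scores at T0 and T1 are uncorrelated"), the change score has twice the variance of a single score.

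The protocol itself fixes the model, so this is not a detail left to the SAP. Two things are at stake: the width of the interval around the one confirmatory estimate, and how far that estimate depends on the two arms happening to start at similar MAI levels. The more precise analysis is already planned, but it cannot carry the confirmatory conclusion if the two results differ.

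**Working it through.** **Inputs (protocol 12.3):** SD of change 6; d=0.3; two-sided α=0.05; ICC 0.03; 7 patients per practice; 31 practices (217 patients) per arm; pilot SD of change 5.2.

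**Step 1: reproduce the plan's figure.** Design effect = 1 + 6 × 0.03 = 1.18. The standard error in SD units is √(2 × 1.18/217) = 0.1043, so the noncentrality is 0.3/0.1043 = 2.877. A noncentral t with 2 × (31 − 1) = 60 df gives power 80.8%. With 30 practices per arm it is 79.5%. The smallest number reaching 80% is therefore 31 per arm, which matches the stated 62 practices and 434 patients exactly.

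**Step 2: variance ratio.** Let σ be the SD of MAI at one visit (assumed equal at T0 and T1) and r the T0–T1 correlation (assumed the same within and between practices).
- Change score: Var = 2σ²(1 − r)
- Baseline-adjusted: Var = σ²(1 − r²) = σ²(1 − r)(1 + r)
- Ratio, adjusted to change score: (1 + r)/2

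The ratio is below 1 for every r below 1, so the direction of the gain does not depend on the value of r. The size does.

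**Step 3: range over r.** CI width scales with √[(1+r)/2]. For power, the SD of change stays at 6 and the design effect at 1.18, so d=0.3 becomes 0.3/√[(1+r)/2] in the same noncentral t with 60 df.

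| r | variance ratio | CI narrower by | power at planned d=0.3 |
|---|---|---|---|
| unadjusted | 1 | – | 80.8% |
| 0 | 0.50 | 29% | 97.9% |
| 0.25 | 0.625 | 21% | 94.7% |
| 0.5 | 0.75 | 13% | 90.5% |
| 0.7 | 0.85 | 8% | 86.6% |

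The r=0.25 row is an assumption. If σ = 6/√2 = 4.24 (the value r=0 implies), the pilot SD of change gives r = 1 − 5.2²/(2 × 18) = 0.249. The protocol reports no single-visit SD, so this is only one point in the range.

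At an SD of 6, d=0.3 is 1.8 units. For the full 2 units (2/6 = 0.333), power at r=0 goes from 88.2% to 99.4%.

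**Step 4: chance baseline imbalance.** A baseline difference D between arms moves the change-score estimate by −(1 − r)D relative to the adjusted one. Take r=0:
- SE of the change-score estimate: 6 × 0.1043 = 0.626
- SE of the adjusted estimate: 4.24 × 0.1043 = 0.442
- One SE of D: 4.24 × 0.1043 = 0.442, shifting the estimate by 0.442

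Then 0.442² + 0.442² = 0.391 = 0.626². The shift accounts exactly for the difference between the two standard errors, so it is the same loss as in Step 3 seen from another side.

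**The case against.** The strongest defence is that nothing here is wrong. Endpoint, hypothesis, model and sample size all rest on the change score and agree with each other. Under randomisation the unadjusted comparison is unbiased with the right type I error, and the baseline-adjusted result is prespecified. All of this stands. It makes the point one of efficiency rather than validity.

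A reader might infer three stronger things that the documents do not support.

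- **That the change score will double the variance, so half the sample is wasted.** The doubling holds only at r=0, which section 12.3 calls conservative and uses to push the SD of change upwards. It is not an expected correlation. At r=0.7 the interval narrows by only 8%.
- **That baseline imbalance is a further bias on top of the precision loss.** Step 4 shows that it is already inside the change-score standard error. Setting 0.44 units beside the pilot effect of 0.4 also exaggerates it. The trial treats 2 units as relevant, and 0.44/2 is 22% of that.
- **That baseline MAI is certain to exist for every patient.** Section 8.1.1 feeds interview symptoms into the rating, and 11.2.2 allows that interview to be missing. This does not count against adjustment, because a patient without a T0 score has no change score either.

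One part of the defence fails. A cautious SD is a good reason for a larger sample, but not for choosing the less precise confirmatory model.

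**Conclusion.** The point holds as a free improvement. The confirmatory model leaves out a covariate that is already collected, precedes disclosure of allocation and would sharpen the primary estimate for any r below 1. The gain in CI width runs from 29% (r=0) to 8% (r=0.7), and power at d=0.3 rises from 80.8% to between 97.9% and 86.6%. Adjustment also removes the shift that a chance baseline difference would cause, as part of that same gain.

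The figures assume equal SDs at T0 and T1, one correlation at both levels and an unchanged design effect of 1.18. Confidence is high in the direction and limited in the size, because the protocol gives neither an expected correlation nor a single-visit SD. The planned test remains valid, and the sample size remains correct for it.

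**What to change.** In section 12.2 and the Statistics entry of the synopsis, define the primary model as MAI T1–T0 on treatment group (fixed), baseline MAI (fixed covariate) and practice (random). Move the model without baseline MAI to the sensitivity analyses.

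The treatment coefficient is still the between-group difference in MAI T1–T0, and it is identical whether T1 or T1–T0 is the outcome once T0 is in the model. Endpoint, hypothesis, estimand and sample size do not change, and no data are added or lost. Section 12.2 applies the primary approach to the secondary endpoints too, so the amended text should say whether each of those carries its own baseline value.

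The cost is one sentence in each of the two places.

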4 STUDY DESIGN

PRIMUM is scheduled as a pragmatic, cluster-randomised controlled trial with the general practice as the unit of randomisation. A clustered design (practices as clusters) was chosen to reduce treatment group contamination, since HCA and GP trained in the intervention will plausible not be able to provide usual care.

Allocation concealment will be disclosed after completion of the baseline documentation for all study patients within a practice but before the intervention begins. Intervention will take place on practice level.

Due to the type of intervention, neither GPs and their patients nor the PRIMUM study team will be blinded to the treatment allocation. However, allocation will neither be revealed to the pharmacologist who is responsible for the MAI rating nor to the study statistician who is responsible for the statistical analyses.

To reduce the contamination of the control group only general information of the treatment in the intervention group is provided in the regular study protocol (a complex intervention including a checklist based pre-consultation interview by the HCA and the use of an internet based CDSS). Detailed information about the intervention treatment is provided only to the intervention group as an appendix to the study protocol in the intervention training.

All primary and secondary outcomes will be measured at patient level at baseline (T0), and at follow-up: 6 months after baseline (T1) and 9 months after baseline (T2).

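### The two-sample t-test planned as a sensitivity analysis of MAI change appears to ignore practice clustering, so it would overstate the precision of the result it is meant to help interpret

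*Protocol*

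**What the plan says.** Section 4 sets the design: "PRIMUM is scheduled as a pragmatic, cluster-randomised controlled trial with the general practice as the unit of randomisation". Outcomes are measured on patients. Section 12.2 draws the consequence for the main analysis: "Because of the cluster randomisation, the primary efficacy analysis will use a multilevel regression approach with patients at level one and practices at level two".

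Section 12.2 then lists sensitivity analyses. The first adds practice and patient baseline covariates to the multilevel model. The next is the point at issue: further sensitivity analysis "will include an unadjusted two-sample t -test on change in MAI from baseline to 6 months after baseline". No cluster summary, design-effect correction or robust standard error is attached to it. Its role is stated with that of the others: "Results from these sensitivity analyses will serve to explain and interpret the results of the primary analysis".

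Two further statements bear on the point. Section 12.3 sizes the trial with an ICC of 0.03, an average of 7 patients per practice and a resulting design effect of 1.18, and gives 0.01 as the ICC assumed for general practice. Section 12.2 also states: "Only the result of the primary efficacy analysis will be interpreted in a confirmatory manner".

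**The concern.** A sensitivity analysis is useful when it varies an assumption that could reasonably be made otherwise. This one swaps a feature that the design requires, correlation within practices, for independence between patients, which the protocol rejects in both its primary model and its sample size.

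With equal practice sizes, the multilevel model with treatment alone and the patient-level t-test give the same estimated difference. They differ only in the standard error, and for any positive ICC the t-test's is too small. Agreement between the two therefore says little about robustness, and a disagreement would mainly show that clustering had been left out. What is at stake is the reading of a borderline result: a multilevel p-value just above 0.05 could stand beside a t-test p-value below 0.05 for no other reason.

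**Working it through.** **Inputs (Protocol 12.2 and 12.3).** Two-sided alpha 0.05; power 0.80; d = 0.3; SD of change about 6 MAI units; ICC 0.03, with 0.01 also cited; 7 patients per practice; 31 practices and 217 patients per arm.

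**Step 1: the plan's own figures.**
- Design effect: DEFF = 1 + (7 − 1) × 0.03 = 1.18, as stated.
- Sample size: the standard error in SD units is sqrt(2 × DEFF / (7K)) with K practices per arm, and power comes from the noncentral t distribution with 2K − 2 df. K = 30 gives power 0.795 and K = 31 gives 0.808. So 31 practices and 217 patients per arm is the smallest design that reaches 0.80, and the stated size reproduces. The planning calculation does allow for clustering.

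**Step 2: true error of a t-test that ignores clustering.** The true variance of the difference is DEFF times what the test assumes, so

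true two-sided error = 2 × (1 − Φ(1.96 / sqrt(DEFF))), and interval width relative to the correct width = 1 / sqrt(DEFF).

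| ICC | Source | DEFF | True error | 95% CI too narrow by |
|---|---|---|---|---|
| 0.01 | Protocol 12.3 | 1.06 | 5.7% | 3% |
| 0.03 | Protocol 12.3 | 1.18 | 7.1% | 8% |
| 0.05 | assumption | 1.30 | 8.6% | 12% |
| 0.10 | assumption | 1.60 | 12.1% | 21% |

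The last two rows only show how the error grows. Those ICCs are not in the protocol.

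**Step 3: the same in MAI units at ICC 0.03.**
- Half-width reported by the t-test: 1.96 × 6 × sqrt(2/217) = 1.13.
- Half-width allowing for clustering: 1.96 × 6 × sqrt(2 × 1.18/217) = 1.23.
- Actual coverage of the nominal 95% interval: about 92.9%.
- A correct p of 0.050 would be shown as 2 × (1 − Φ(1.96 × sqrt(1.18))) = 0.033. Correct p-values between 0.05 and about 0.07 would be shown as below 0.05.

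**Step 4: simulation.** There were 20,000 null trials per ICC, with 31 practices of 7 patients per arm.

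| ICC | Patient-level t-test | t-test on practice means |
|---|---|---|
| 0.01 | 5.8% | 5.1% |
| 0.03 | 7.1% | 5.1% |
| 0.10 (assumption) | 12.2% | 5.0% |

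A separate run of 20,000 trials at ICC 0.03 gave 6.8% and 4.7%. The simulations agree with the formula, and the practice-mean test holds its level.

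**The case against.** **The test may not be at patient level.** The protocol does not say whether patients or practice means enter it. The word unadjusted follows a sentence on covariates and could mean only that no covariates are used. Section 12.3 uses the term two-sample t-test for a calculation that does allow for clustering, and section 12 defers detail to a SAP that is not available here. This stands as a caveat, but it is not the natural reading. The endpoint is each patient's change, and the contrast is with a multilevel model. Section 12.3 applies the design effect expressly, whereas this sentence applies nothing. If practice means were intended, the sentence still needs to say so.

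**The protocol already limits the harm.** This stands. A reader might infer that a significant t-test could rescue a non-significant primary result, or that the trial's own type I error is 7.1%. Neither is supported: the confirmatory reading is confined to the multilevel analysis, and the trial is sized for clustering. Nor does the text present this test as support for the primary result. It attaches that aim to the covariate-adjusted models and gives the t-test an explanatory role.

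**The error is not in the intervention's favour.** This also stands. A reader might infer bias towards benefit. Ignoring clustering does not bias the estimate, and under the null the excess of about 2 percentage points splits equally between false benefit and false harm. The fault is overstated precision.

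**Comparing clustered with unclustered results shows what clustering did.** This is a weak use. The ICC, which section 12.2 already reports, conveys it without a misleading p-value.

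**Conclusion.** The point holds in limited form. As naturally read, the planned t-test ignores the clustering that the protocol recognises elsewhere. Its p-value and interval are therefore wrong as a check on the primary result. On the protocol's own ICCs, the true error is 5.7% (ICC 0.01) to 7.1% (ICC 0.03), and the 95% interval is 3% to 8% too narrow. A reader might take the larger figures at ICC 0.05 or 0.10 as expected, but the protocol does not support that: it calls 0.03 conservative.

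The figures assume that patients enter the test, that practices contribute equal numbers, and that the ICC is positive. The primary model, the sample size and the confirmatory conclusion are untouched. The sentence should be corrected because the test has a stated part in interpreting the primary result, and a valid test is just as simple.

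**What to change.** Replace the t-test sentence in section 12.2 with a two-sample t-test on practice-mean changes in MAI. This has 60 df with 62 practices and 68 with 70. Weight by practice size if sizes differ, because unweighted means count every practice equally and can shift the quantity estimated away from the average over patients. A patient-level comparison with cluster-robust standard errors would also do. Either gives a real check on the multilevel model's assumptions while respecting the unit of randomisation.

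If the patient-level comparison is kept, state that it is descriptive and report it without an inferential p-value. If practice means were intended all along, say so.

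The cost is one sentence, with a matching line in the SAP. No data collection, sample size or primary analysis changes.
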